**APPENDIX**

[figure not shown]
**Patient global assessment of disease activity**

Considering all the ways that your rheumatoid arthritis affects you, rate how you are doing on the following scale by placing a vertical mark on the line:

	
Very well	Very poor
0 mm	100 mm

**Physician global assessment of disease activity**

Place a vertical mark on the line for how you would assess your patient's current activity

	
Very well	Very poor
0 mm	100 mm

## Appendix C Other specific appendices for a given clinical trial

### New York Heart Association Classification of Heart Failure

Class	Patient Symptoms
Class I (Mild)	No limitation of physical activity. Ordinary physical activity does not cause undue fatigue, rapid/irregular heartbeat (palpitation) or shortness of breath (dyspnea).
Class II (Mild)	Slight limitation of physical activity. Comfortable at rest, but ordinary physical activity results in fatigue, rapid/irregular heartbeat (palpitation) or shortness of breath (dyspnea).
Class III (Moderate)	Marked limitation of physical activity. Comfortable at rest, but less than ordinary activity causes fatigue, rapid/irregular heartbeat (palpitation) or shortness of breath (dyspnea).
Class IV (Severe)	Unable to carry out any physical activity without discomfort. Symptoms of fatigue, rapid/irregular heartbeat (palpitation) or shortness of breath (dyspnea) are present at rest. If any physical activity is undertaken, discomfort increases.

## APPENDIX

### National Cholesterol Education Program Adult Treatment Panel III

*National Cholesterol Education Program*

# ATP III Guidelines At-A-Glance Quick Desk Reference

- 1**  
**Step 1** Determine lipoprotein levels—obtain complete lipoprotein profile after 9- to 12-hour fast.

#### ATP III Classification of LDL, Total, and HDL Cholesterol (mg/dL)

##### LDL Cholesterol – Primary Target of Therapy

<100	Optimal
100-129	Near optimal/above optimal
130-159	Borderline high
160-189	High
≥190	Very high

##### Total Cholesterol

<200	Desirable
200-239	Borderline high
≥240	High

##### HDL Cholesterol

<40	Low
≥60	High

- 2**  
**Step 2** Identify presence of clinical atherosclerotic disease that confers high risk for coronary heart disease (CHD) events (CHD risk equivalent):

- Clinical CHD
- Symptomatic carotid artery disease
- Peripheral arterial disease
- Abdominal aortic aneurysm.

- 3**  
**Step 3** Determine presence of major risk factors (other than LDL):

#### Major Risk Factors (Exclusive of LDL Cholesterol) That Modify LDL Goals

Cigarette smoking
Hypertension (BP ≥140/90 mmHg or on antihypertensive medication)
Low HDL cholesterol (<40 mg/dL)*
Family history of premature CHD (CHD in male first degree relative <55 years; CHD in female first degree relative <65 years)
Age (men ≥45 years; women ≥55 years)

\* HDL cholesterol ≥60 mg/dL counts as a "negative" risk factor; its presence removes one risk factor from the total count.

- Note: in ATP III, diabetes is regarded as a CHD risk equivalent.

**APPENDIX**  
SmPC sarilumab

- COX-2: Cyclo-Oxygenase-2 Inhibitors
- csDMARD: Conventional synthetic Disease-Modifying Anti-Rheumatic Drug
- DAS28: Disease Activity Score in 28 joints
- DD: Derived Data
- DMARD: Disease-Modifying Anti-Rheumatic Drug
- Dx Day x
- ECG: Electrocardiogram
- ESR: Erythrocyte Sedimentation Rate
- EULAR: European League Against Rheumatism
- FACIT-F: Functional Assessment of Chronic Illness Therapy – Fatigue
- HADS: Hospital Anxiety and Depression Scale
- HAQ-DI: Stanford Health Assessment Questionnaire - Disability Index
- HBsAg: Hepatitis B surface antigen
- HCV: Hepatitis C Virus
- ICF: Informed Consent Form
- IMP: Investigational Medicinal Product
- IPAQ : International Physical Activity Questionnaire
- ITT: Intent-To Treat

- LTE: Long-Term Extension
- MATHys: Multidimensional Assessment of Thymic States
- MedDRA: Medical Dictionary for Regulatory Activities
- NSAID: Non-Steroidal Anti-Inflammatory Drugs
- PPS: Per Protocole Set
- PRO: Patient-Reported Outcomes
- PT: Preferred Term
- RA: Rheumatoid Arthritis
- RAID: Rheumatoid Arthritis Impact of Disease
- SAE: Serious Adverse Event
- SAF: Safety Population
- SAP: Statistical Analysis Plan
- SD: Standard Deviation
- SJC: Swollen Joints
- SOC: System Organ Class
- TB: Tuberculosis
- TJC: Tender Joints
- TNF: Tumor Necrosis Factor
- ULN: Upper Limit of Normal
- VAS: Visual Analogue Scale
- Vx: Visit x
- WHO - DD: World Health Organization - Drug Dictionary
- Wx: Week x

1. OVERVIEW AND STUDY PLAN

[figure not shown]
This Statistical Analysis Plan (SAP) provides a comprehensive and detailed description of strategy and statistical technique to be used to realize the analysis of data for study SariPRO SARILL08755.

1.1. STUDY DESIGN

SariPRO is a national, multicenter, open-label, single-arm phase IV study. The total duration of the core study period per patient expected to be approximately 32 weeks:

Four study periods are defined for this study:

- Screening period: within 28 days prior to study treatment start (Baseline visit, Day 1 (D1)).
- 6-month core period: 3 visits are scheduled (W4, W12 and W24).
- Long-Term Extension (LTE) period: for all the patients who will complete the 6-month-core-period (allowed to continue the treatment with sarilumab). Patient visits are scheduled every 12 weeks over the LTE period (at W36 and W48).
- Post-treatment follow-up: each patient will have one follow-up visit, between 2 and 4 weeks after his/her last administration of sarilumab.

* Patients who will complete the 6-month-core-period will be allowed to continue the treatment with sarilumab, every 2 weeks for a maximum of another 24 weeks or until the commercial availability of sarilumab, depending whichever comes first.

Figure 1: Graphical study design

1.2. OBJECTIVES

1.2.1. Primary objectives (6-months core period)

The primary objective of this study is to describe the evolution of the perception of patients regarding the effect of sarilumab in combination with conventional synthetic Disease-Modifying Anti-Rheumatic Drug (csDMARD) and/or monotherapy on patient-reported impact of disease, using the rheumatoid arthritis impact of disease (RAID) questionnaire, in patients with moderately to severely active rheumatoid arthritis (RA) and inadequate response or intolerance to current csDMARD or tumor necrosis factor (TNF) inhibitors.

1.2.2. Secondary objectives (6-months core period)

The secondary objectives of this study are:

- To assess the change of the RAID score from baseline (to Week 4 (W4) and W12) in patients with moderately to severely active RA and inadequate response or intolerance to current csDMARD or TNF inhibitors, treated with sarilumab in combination with csDMARD and/or monotherapy.
- To assess the effect of sarilumab in combination with csDMARD and/or monotherapy on other patient-reported outcomes (global assessment of disease activity, disability, morning stiffness, fatigue, anxiety/ depression, mood disorders, and physical activities), in patients with moderately to severely active RA and inadequate response or intolerance to current csDMARD or TNF inhibitors.
- To assess the efficacy of sarilumab in combination with csDMARD and/or monotherapy using Disease Activity Score in 28 joints-Erythrocyte Sedimentation Rate (DAS28-ESR) and Clinical Disease Activity Index (CDAI) in patients with moderately to severely active RA and inadequate response or intolerance to current csDMARD or TNF inhibitors.
- To assess the safety of sarilumab in combination with csDMARD and/or monotherapy in patients with moderately to severely active RA and inadequate response or intolerance to current csDMARD or TNF inhibitors.

1.2.3. Exploratory objectives

The exploratory objectives of this study are:

Over the 6-month core period

- To describe the associations between changes in RAID score and composite disease activity scores (DAS28-ESR and CDAI).
- To describe the associations between changes in Hospital Anxiety and Depression Scale (HADS) score and in composite disease activity scores (DAS28-ESR and CDAI)
- To explore patient profiles

Over the long-term extension (LTE) period (maximum 24 weeks)

- To assess the safety of sarilumab in combination with csDMARD and/or monotherapy in patients with moderately to severely active RA and inadequate response or intolerance to current csDMARD or TNF inhibitors over the LTE period. This objective will be considered as a **safety objective** for the rest of the document.

1.3. ENROLMENT OF CENTRES AND PATIENTS

Inclusion criteria:

- I 01.** Patient with moderately to severely active RA according to the 2010 American College of Rheumatology (ACR)/European League against Rheumatism (EULAR) criteria
- I 02.** Patient with moderate to severe disease activity defined as DAS28-ESR>3.2 at Screening
- I 03.** Patients with inadequate response within at least the last 3 months or intolerance to current csDMARD or to at least one anti-TNF therapy (as defined by the investigator)
- I 04.** Oral corticosteroids (≤ 15 mg/day prednisone or equivalent) and non-steroidal anti-inflammatory drugs (NSAID) or cyclo-oxygenase-2 inhibitors (COX-2) (up to the maximum recommended dose) are allowed if at a stable dose for at least 4 weeks prior to Baseline
- I 05.** Permitted csDMARDs are allowed if at a stable dose for at least 4 weeks prior to Baseline
- I 06.** Patients able and willing to give written informed consent and to comply with the requirements of the study protocol.

Exclusion criteria:

- E 01.** <18 years of age
- E 02.** Patient unable to understand and write adequately to complete the study Patient Reported Outcomes (PRO) assessments
- E 03.** Exposure to sarilumab at any time prior to Baseline
- E 04.** Use of intra-articular or parenteral corticosteroids within 4 weeks prior to Baseline
- E 05.** Treatment with any investigational agent within the 4 weeks of Screening
- E 06.** Last RA treatment prior to inclusion with any antiJAK or biologic DMARD other than anti-TNF
- E 07.** Patients treated with anti-TNF (e.i. adalimumab, infliximab, certolizumab, golimumab, etanercept) before the screening period, which are maintained within the 4 weeks before the inclusion (i.e.the first injection of sarilumab)
- E 08.** Rheumatic autoimmune disease other than RA or prior history or current inflammatory joint disease other than RA

- E 09.** Evidence of active malignant disease, malignancies diagnosed within the previous 10 years (except basal and squamous cell carcinoma of the skin or carcinoma in situ of the cervix uteri previously excised and cured)
- E 10.** Patient who is institutionalized due to regulatory or legal order or patient who is mentally disabled or educationally disadvantaged
- E 11.** Pregnant or breastfeeding woman
- E 12.** Women of childbearing potential not protected by highly-effective contraceptive method(s) of birth control (as defined in the informed consent form and/or in a local protocol addendum/amendment) over the study period and for at least 3 months following the last dose of sarilumab, and/or who are unwilling or unable to be tested for pregnancy
- E 13.** History of severe allergic or anaphylactic reactions to human, humanized, or murine monoclonal antibodies (or to any of the excipients associated to sarilumab)
- E 14.** Immunization with a live/attenuated vaccine within 4 weeks prior to Baseline
- E 15.** Stage III or IV cardiac failure according to the New York Heart Association classification
- E 16.** History of previous gastrointestinal perforation or diverticulitis
- E 17.** Known active current/ recurrent infections (including but not limited to active tuberculosis (TB) or history of incompletely treated TB and atypical mycobacterial disease, hepatitis B and C, and herpes zoster)
- NOTE: in case of latent TB infection the patient may be included if a subsequent appropriate anti TB treatment is initiated since at least 3 weeks
- E 18.** Positive hepatitis B surface antigen (HBsAg), and/or positive total hepatitis B core antibody, and/or positive hepatitis C antibody (HCV) at the Screening visit
- E 19.** Evidence of serious uncontrolled concomitant disease, including severe uncontrolled hypercholesterolemia or hypertriglyceridemia
- E 20.** Patients with any of the following laboratory abnormalities at the Screening or Baseline visit:
- Hemoglobin <8.5 g/dL
 - White blood cells <3000/mm³
 - Absolute neutrophil count <2000/mm³
 - Absolute lymphocyte count <500/mm³
 - Platelet count <150 000 cells/mm³
 - AST or ALT >1.5 x Upper Limit of Normal (ULN)
 - Bilirubin (total) >ULN, unless Gilbert's disease has been determined by genetic testing and has been documented
 - Total fasting cholesterol >3.50 g/L [9.1 mmol/L] or triglycerides >5.00 g/L [5.6 mmol/L]

Selection criteria (LTE period):

All the patients who will complete the 6-month-core period will be allowed to enter the LTE period, if sarilumab is not yet commercially available in France (as monotherapy or in combination with csDMARDs).

1.4. DETERMINATION OF SAMPLE SIZE

The primary study objective is to assess the change in **RAID** score from baseline to W24. A sufficient precision (half-length of the 95% confidence interval (CI)) is required. According to the literature [\[1,2,3\]](#) and findings from the MONARCH and TARGET studies [\[4,5\]](#), the standard deviation (SD) of the **RAID** score could be estimated at 2.5 points. On this basis, a sample size of 140 patients (122 evaluable, if 20% non-evaluable patients) produces a precision, two-sided 95% confidence interval (CI), with a distance from the mean to the limits that will be less than 0.5 when the estimated SD is 2.5. Table below gives the 95% CI of change from baseline to W24 of **RAID** score with this precision (0.44), assuming that the change from baseline will be from 30% to 50% (MCII defined by Dougados [\[6\]](#) in 2012) of baseline score.

1.5. STUDY PLAN

The data are recorded prospectively during one baseline visit, one follow-up visit at week 4 ± 3 days, a second follow-up visit at 12 ± 1 week, a third follow-up visit at 24 ± 1 week.

For the LTE period, data are recorded prospectively during one follow-up visit at 36 ± 1 week and a second follow-up visit at 48 ± 1 week.

	Screening	Treatment						Post-treatment observations	Early withdrawal
		6-month core period				Long-term extension period			
VISIT	V1	V2 (Baseline)	V3	V4	V5	V LTE1	V LTE2	V PT	
DAY / WEEK	D-28 to D-1	D1	W4 ±3D	W12 ±7D	W24 ±7D	W36 ±7D	W48 ±7D	2 to 4 weeks after the last IMP administration	
Eligibility									
Written Informed Consent	X								
Inclusion/Exclusion criteria	X	X							
Patient demography ^a	X								
Medical/surgical history	X								
Prior medication history	X								
Physical examination ^b	X				X				X
12-lead ECG and Chest X-ray ^c	X								
Treatment									
IMP administration ^d		←-----→				←-----→			
Concomitant medication review		X	X	X	X	X	X	X	X
Compliance / review patient diary			X	X	X	X	X	X	X
Patient Reported Outcomes									
RAID, HADS, MATHyS, FACIT-Fatigue, HAQ-DI, duration of morning stiffness, IPAQ, and patient global assessment of disease activity (VAS)		X	X	X	X				X
Efficacy									
ESR, DAS28-ESR, CDAI, and joint counts (TJC and SJC on 28 joints) ^e	X	X	X	X	X				X
Size of the largest rheumatoid nodule (if applicable)		X			X				X
Safety									
AE/SAE recording ^f		←-----→							
Vital signs ^g	X	X	X	X	X	X	X	X	X

Pregnancy test (for women of childbearing potential) ^h	X	X	X	X	X	X	X	X	X
Hematology ^l	D-7 to D-1		X	X	X	X	X		X
Serum chemistry ^l	D-7 to D-1		X	X	X	X	X		X
Serum iron, 25OHD ^k	X				X				X
Fasting lipids ^l	D-7 to D-1		X	X	X	X	X		X
Serology ^m	X								
Tuberculosis assessment ⁿ	X								

a) Gender and age.
b) A general physical examination should be performed during the Screening period (between D-28 and D-1). Body weight and waist circumference are to be recorded only at V2 and V5 (and at early withdrawal if applicable).
c) If at Baseline a chest X-ray has been taken within 90 days that shows no clinically significant abnormality, a further chest X-ray is not required. A 12-lead ECG should be performed during the Screening period.
d) Sarilumab 200 mg SC q2w, as monotherapy or in combination with a csDMARD (at Investigator's discretion). The first SC injection will be administered at the hospital site under supervision of the Investigator. For patients and/or non-professional caregivers able to perform SC injections at home, the investigator or delegate will provide training regarding the preparation and injections (at Baseline). For patients and/or non-professional caregivers completely unable to perform such injections at home, a home nursing will be needed.
e) Self-reported questionnaires should be completed by the patient before all other assessments performed during the study visits (and before the IMP administration if performed at this time).
f) All adverse events (date of onset, seriousness, maximum intensity, causal relationship with sarilumab, events leading to treatment modification or discontinuation, outcome of events).
g) Pulse rate, systolic and diastolic blood pressure (while seated).
h) Pregnancy tests will be locally conducted for female patients of child-bearing potential. Pregnancy test at Screening will be a serum test. All following pregnancy tests will be urine tests. If a urine test is positive it must be confirmed by a serum pregnancy test.
i) Hemoglobin, complete blood count (CBC), platelet count, and erythrocyte sedimentation rate (ESR) (blood should be drawn before drug administration). First tests will be performed during the 7-day period before inclusion. All tests will be performed locally.
j) Creatinine clearance, alanine aminotransferase (ALT), aspartate aminotransferase (AST), total bilirubin (blood should be drawn before drug administration). First tests have to be performed during the 7-day period before inclusion. All tests will be performed locally.
k) Blood should be drawn before drug administration. First tests will be performed during the Screening period. All tests will be performed locally.
l) Total fasting cholesterol, high density lipoprotein (HDL) cholesterol, low density lipoprotein (LDL) cholesterol, triglycerides (blood should be drawn before drug administration). First tests have to be performed during the 7-day period before inclusion. All tests will be performed locally.
m) HBsAg, hepatitis B virus antibody and hepatitis C virus antibody will be performed during the Screening period only, unless clinically indicated during the trial.
n) If at Baseline a tuberculosis assessment (QUANTIFERON) has been taken within 90 days that shows no abnormality, a further QUANTIFERON test is not required. Further tuberculosis assessments are not required unless clinically indicated during the trial.

Figure 2: Study flow-chart

1.6. MODIFICATIONS FROM THE PROTOCOL

Analysis sets definition have been reviewed:

Population	Protocol definition	Statistical analysis plan definition
Enrolled patients	No definition	All patients screened, who have signed the Informed Consent Form (ICF) and who never took the study treatment at any time before baseline.
Intent-to-treat (ITT) population	All patients who met all the eligibility criteria and who are actually treated.	All patients included (i.e. for whom the inclusion decision "Has the decision to include the patient been taken" is 'Yes') and who took the treatment at least once
Per-protocol population	Patients of ITT population without major protocol deviations. Major deviations will be defined in the statistical analyses plan before database frozen.	Patients of ITT population without major protocol deviations as defined during the Data Review meeting and who are evaluable for the main criterion

Data will be presented according to a subgroup not defined in the protocol. This subgroup has 3 categories^{DD}:

- Patients treated with csDMARDs for whom Sarilumab is prescribed in addition to csDMARDs at baseline.
- Patients treated with biological therapy for whom Sarilumab is prescribed in addition to csDMARDs at baseline.
- Patients previously treated with csDMARDs or biological therapy for whom only Sarilumab in monotherapy is prescribed at baseline.

Also, an analysis has been performed with all screened patients who have met all the eligibility criteria and who have received the treatment at baseline visit (D1). Only data from the baseline visit have been analysed.

In the protocol section 11.4.1.3, compliance should be evaluated according to the planned dose required by the protocol. No planned dose is required by the protocol. Hence, compliance will be evaluated according to the number of injections during the study (see section 5.1.4).

Adverse events will not be described by SOC, HLG, HLT and PT but only by SOC and PT.

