--	---

	
B and C hepatitis)
 
NOTE: in case of latent TB infection the patient may be included if a subsequent appropriate anti TB treatment is initiated since at least 3 weeks
 
 
• Active tuberculosis or history of incompletely treated tuberculosis
 
• Evidence of serious uncontrolled concomitant disease, including severe uncontrolled hypercholesterolemia or hypertriglyceridemia at Screening
 
• Hemoglobin <8.5 g/dL at Screening
 
• Creatinine clearance <30 mL/min at Screening
 
• White blood cells <3000/mm^3 at Screening
 
• Absolute neutrophil count <2000/mm^3 at Screening
 
• Absolute lymphocyte count <500/mm^3 at Screening
 
• Platelet count <150 000 cells/mm^3 at Screening
 
• AST or ALT >1.5 x ULN at Screening
 
• Total bilirubin >ULN at Screening, unless Gilbert's disease has been determined by genetic testing and has been documented
 
• Total fasting cholesterol >3.50 g/L [9.1 mmol/L] or triglycerides >5.00 g/L [5.6 mmol/L] at Screening.
 

Total expected number of patients	140 patients enrolled in 35 university hospitals and general hospitals centers are expected throughout mainland France.
STUDY TREATMENT(s)	
Investigational medicinal product(s)	Sarilumab, anti-IL6R mAb (anti-interleukin 6 receptor monoclonal antibody)
Formulation:	Single-use prefilled glass syringes of sarilumab 200 mg (and 150 mg in case of laboratory abnormalities)
Route(s) of administration:	Subcutaneous (SC) route, in abdomen, thigh, or upper arm
Dose regimen:	Sarilumab 200 mg is to be administered every 2 weeks (q2w) over the both treatment periods (as monotherapy or in combination with a csDMARD according to the investigator decision).
Non-investigational medicinal product(s)	NA
Formulation:	
Route(s) of administration:	
Dose regimen:	
Post-trial access to study medication	NA

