d) Sarilumab 200 mg SC q2w, as monotherapy or in combination with a csDMARD (at Investigator's discretion). The first SC injection will be administered at the hospital site under supervision of the Investigator. For patients and/or non-professional caregivers able to perform SC injections at home, the investigator or delegate will provide training regarding the preparation and injections (at Baseline). For patients and/or non-professional caregivers completely unable to perform such injections at home, a home nursing will be needed.

e) Self-reported questionnaires should be completed by the patient before all other assessments performed during the study visits (and before the IMP administration if performed at this time).

f) All adverse events (date of onset, seriousness, maximum intensity, causal relationship with sarilumab, events leading to treatment modification or discontinuation, outcome of events).

g) Pulse rate, systolic and diastolic blood pressure (while seated).

h) Pregnancy tests will be locally conducted for female patients of child-bearing potential. Pregnancy test at Screening will be a serum test. All following pregnancy tests will be urine tests. If a urine test is positive it must be confirmed by a serum pregnancy test.

i) Hemoglobin, complete blood count (CBC), platelet count, and erythrocyte sedimentation rate (ESR) (blood should be drawn before drug administration). First tests will be performed during the 7-day period before inclusion. All tests will be performed locally.

j) Creatinine clearance, alanine aminotransferase (ALT), aspartate aminotransferase (AST), total bilirubin (blood should be drawn before drug administration). First tests have to be performed during the 7-day period before inclusion. All tests will be performed locally.

k) Blood should be drawn before drug administration. First tests will be performed during the Screening period. All tests will be performed locally.

l) Total fasting cholesterol, high density lipoprotein (HDL) cholesterol, low density lipoprotein (LDL) cholesterol, triglycerides (blood should be drawn before drug administration). First tests have to be performed during the 7-day period before inclusion. All tests will be performed locally.

m) HBsAg, hepatitis B virus antibody and hepatitis C virus antibody will be performed during the Screening period only, unless clinically indicated during the trial.

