### 6.2 DURATION OF STUDY PARTICIPATION

#### 6.2.1 Duration of study participation for each patient

The total duration of the 6-month core study period per patient is expected to be approximately 32 weeks:

- Up to 4-week for screening
- 24 weeks for the treatment period (sarilumab 200 mg q2w)
- Between 2 and 4 week for post-treatment observations.

For patients who will enter in the LTE period, a maximum of another 24 weeks is planned.

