## 8 STUDY TREATMENTS

### 8.1 INVESTIGATIONAL MEDICINAL PRODUCT

The investigational medicinal product (IMP) is sarilumab (Kevzara®) that is expected to be available commercially in the second half of 2018 in France.

Sarilumab will be supplied by the Sponsor in 1.14 mL ready-to-use, single-use prefilled glass syringes delivering 200 mg (175 mg/mL) of sarilumab for subcutaneous (SC) injections. A patient will use one prefilled syringe for each dosing. In case of specific laboratory abnormalities over the treatment period (see section 10.4.6 for more details), the Sponsor will supply 1.14 mL ready-to-use, single-use prefilled glass syringes delivering 150 mg (131.6 mg/mL) of sarilumab for SC injections, using the Interactive Voice Response System (IVRS).

During the treatment period, the IMP should be administered every 14 days; however an IMP administration window of  $\pm 3$  days is permitted per protocol to accommodate exceptional circumstances, eg, laboratory test result pending), ongoing adverse event, or patient scheduling difficulty.

Patients and/or their non-professional caregivers will be trained to administer IMP at the start of the treatment period. This training must be documented in the patients' study file. The study coordinator or designee may administer the first injection, or allows the patient to self-inject, under observation, and provide feedback on technique, thus combining the initial dose administration as part of the training procedure on Treatment Period Day 1 (Visit 2). If SC injections have to be done on days when the patient has a study visit, the IMP will be administered following clinic procedures and blood collection. For doses not given at the study site, a diary card will be provided to record information pertaining to these injections; these diaries will be kept as source data in the patients' study file.

If a patient or non-professional caregiver is completely unable to administer sarilumab at home, it is permitted that the dose will be administered as described above by a home nurse as scheduled.

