#### 10.4.6 Guidelines for management of specific laboratory abnormalities

Recommended dose modifications in case of neutropenia, thrombocytopenia, or liver enzyme elevations are provided in the following tables.

Low Absolute Neutrophil Count	
Lab Value (cells x 10^9/L)	Recommendation
ANC greater than 1	Current dose of sarilumab should be maintained.
ANC 0.5-1	Treatment with sarilumab should be withheld until >1 x 10  /L. Sarilumab can then be resumed at 150 mg every 2 weeks and increased to 200 mg every 2 weeks as clinically appropriate.
ANC less than 0.5	Discontinue sarilumab.

Low Platelet Count	
Lab Value (cells x 10^3/μL)	Recommendation
50 to 100	Treatment with sarilumab should be withheld until >100 x 10  /μL. Sarilumab can then be resumed at 150 mg every 2 weeks and increased to 200 mg every 2 weeks as clinically appropriate.
Less than 50	If confirmed by repeat testing, discontinue sarilumab.

Liver Enzyme Abnormalities	
Lab Value	Recommendation
ALT >1 to ≤ 3 x ULN	Consider dose modification of concomitant DMARDs as clinically appropriate.

Liver Enzyme Abnormalities	
Lab Value	Recommendation
ALT >3 x and ≤5 x ULN	Treatment with sarilumab should be withheld until < 3 x ULN. Sarilumab can then be resumed at 150 mg every 2 weeks and increased to 200 mg every 2 weeks as clinically appropriate.
ALT >5 x ULN	Treatment with sarilumab should be discontinued.

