#### ***11.4.1.3 Compliance***

A given administration will be considered non-compliant if the patient did not take the planned dose of treatment as required by the protocol. No imputation will be made for patients with missing or incomplete data.

Treatment compliance, above-planned and under-planned dosing percentages will be summarized descriptively (N, mean, SD, median, min, and max). The percentage of patients with compliance <80% will be summarized.

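### SAP 1.6 says the protocol sets no planned dose; it does, and the compliance summaries required by protocol 11.4.1.3 are lost as a result

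*SAP*

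**What the plan says.** The protocol states the regimen as a plan. Its summary reads "Sarilumab 200 mg is to be administered every 2 weeks (q2w) over the both treatment periods". The footnote on drug administration in the flow chart (protocol 1.2) and the duration section (6.2.1) give the same dose and interval. Section 8.1 adds that "the IMP should be administered every 14 days", with a window of 3 days either side. Section 10.4.6 allows a change after certain laboratory abnormalities: "Sarilumab can then be resumed at 150 mg every 2 weeks and increased to 200 mg every 2 weeks as clinically appropriate".

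Protocol 11.4.1.3 judges each administration against the planned dose. It asks for descriptive summaries of compliance and of the percentages dosed above and below plan, and adds: "The percentage of patients with compliance <80% will be summarized".

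SAP 1.6, which lists current departures from the protocol, says "No planned dose is required by the protocol" and concludes that compliance will be assessed by the number of injections, as set out in SAP 5.1.4. Yet footnote d to the flow chart in SAP 1.5 reads "Sarilumab 200 mg SC q2w, as monotherapy or in combination with a csDMARD".

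**The concern.** A departure from the protocol needs a sound reason. The only reason offered here is a statement about the protocol that the protocol contradicts. It matters because the change removes a denominator. A number of injections does not say how many were due, so on its own it cannot show what share of the planned treatment a patient took. The 80% threshold that the protocol set in advance cannot be read from it. A reader of the study report would look for the protocol's compliance results and find no equivalent.

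**Working it through.** The plan states no compliance figure, so there is nothing to reproduce. The check has four parts.

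**1. Is there a planned dose?** The protocol summary, protocol 1.2, protocol 6.2.1 and SAP 1.5 all give 200 mg every 2 weeks; protocol 8.1 gives the 14-day interval. These places agree with one another. The sentence in SAP 1.6 disagrees with all of them.

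**2. What is lost?**

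| Protocol 11.4.1.3 asks for | SAP 5.1.4 and Appendix A provide |
|---|---|
| Each administration judged against the planned dose | Each injection: performed or not, and 150 or 200 mg; no comparison with plan |
| Compliance percentage, summarised over patients | Number of injections per patient; no number due, and no compliance formula among the derived data |
| Percentages dosed above and below plan | Average dose, and whether any increase or decrease occurred; no percentages against plan |
| Share of patients under 80% | Nothing |

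**3. Can a denominator be calculated?** Yes, from SAP Appendix A item 7, where exposure in weeks = (last dose date − first dose date + 14) / 7. Dividing by 2 gives the injections scheduled over that period.

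- Last dose at W22: (154 + 14) / 7 = 24 weeks; 24 / 2 = 12 injections; 12 × 200 = 2400 mg.
- Last dose at W24: (168 + 14) / 7 = 26 weeks; 26 / 2 = 13 injections; 13 × 200 = 2600 mg.

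The week of the last core-period dose is an assumption. Protocol 6.2.2 puts the final visit at W26 to W28 for patients who do not enter the extension, 2 to 4 weeks after the last dose, which fits W24. Over the whole study the same formula gives 24 injections (last dose W46) or 25 (last dose W48).

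The 80% line then falls as follows:

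- 0.8 × 12 = 9.6, so under 80% means fewer than 10 injections.
- 0.8 × 13 = 10.4, so fewer than 11.
- 0.8 × 24 = 19.2, so fewer than 20.
- 0.8 × 25 = 20, so fewer than 20.

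The denominator has to be the patient's own. Ten injections are 10/12 = 83.3% but 10/13 = 76.9%, on opposite sides of the line.

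Two patients with 8 injections each show what a percentage adds. One took 8 consecutive doses and stopped: exposure (98 + 14) / 7 = 16 weeks, 8 scheduled, 8/8 = 100%. The other had a last dose at W22 with 4 missed before it: 8/12 = 66.7%.

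**4. Does the basis matter?** It can. A patient given all 12 injections, 10 of them at 150 mg, is at 12/12 = 100% by injections. By dose the figure is (2 × 200 + 10 × 150) / 2400 = 1900/2400 = 79.2%. With 13 injections, 11 of them at 150 mg, it is (2 × 200 + 11 × 150) / 2600 = 2050/2600 = 78.8%. Neither document says whether a 150 mg injection given under protocol 10.4.6 is the planned dose for the purposes of 11.4.1.3.

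**The case against.** The strongest reply is that little is lost. The SAP declares the change openly and keeps an item called treatment compliance. SAP 5.1.4 also reports exposure duration, temporary interruptions split by reason, definitive interruptions with a listing, average dose, and each injection as performed or not with the reason. SAP 3.1 attaches a percentage and confidence interval to every categorical item. This stands. A reader might infer that an early stopper and a patient who missed doses would look the same under the SAP. That is true of the count alone, but these other outputs separate them. It would likewise be too much to say that the trial cannot describe how much drug was taken.

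A reader might also infer that the per-protocol set is weakened, since it supports the only sensitivity analysis named for the primary endpoint. The documents do not support that. The SAP leaves major deviations to the Data Review meeting, and nothing makes compliance one of the criteria or confines that meeting to the SAP's tables.

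Finally, the permitted change to 150 mg could be said to leave no single planned dose for each patient. The SAP does not give that reason, and it would not make the sentence true. The SAP's own item also tells against it: recording an injection as not performed, with a reason such as forgetting, presupposes that one was due.

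**Conclusion.** Wrong as written; minor severity. The sentence in SAP 1.6 is contradicted by the protocol and by the SAP's own footnote. Because of it, the per-patient compliance percentage, the percentages above and below plan and the under-80% share are not specified for any of the roughly 140 patients planned. The effect stops at a descriptive exposure and compliance output. The RAID change from baseline to W24 is not affected, and there is no documented link to the per-protocol set.

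That the sentence is wrong rests on the text alone. The thresholds in injections rest on the assumed week of the last dose. The example by dose rests on counting 150 mg as below plan, which the documents leave open.

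**What to change.** - Delete the sentence from SAP 1.6.
- Add to Appendix A: compliance (%) = 100 × injections given / injections scheduled, where injections scheduled = exposure in weeks (item 7) / 2, rounded to a whole number because of the 3-day window. Report it for the core period and for the whole study.
- Restore the protocol 11.4.1.3 summaries: the distribution of compliance, the percentages above and below plan, and the share of patients under 80%.
- Have the sponsor reconcile protocol 10.4.6 with 11.4.1.3 by stating whether a 150 mg injection given under 10.4.6 counts as the planned dose, and show those injections separately. This concerns classification in the analysis only, not which dose should be given.

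This denominator does not count doses missed after the last one taken. Those remain visible through the definitive-interruption listing and exposure duration, which should be read alongside it.

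The cost is SAP wording and some programming. Injection counts, dose per injection and first and last dose dates are already used in the SAP. The core-period figure also requires each injection to be assigned to the core or extension period. SAP 5.1.4 lists no date per injection, so the sponsor should confirm that the diary and eCRF records allow this.
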